6.7 Assessment Administration

Due to the time commitment of the MCCB and MRI imaging, these assessments will be completed when clinically feasible. The MCCB and MRI imaging results are not used as part of the screening criteria and are not primary outcome measures. Therefore, while the study staff will attempt to complete these assessments in all participants, failure to complete these assessments will not be exclusionary from the study. Additionally, while the study staff will attempt to complete these assessments prior to the start of antipsychotic medication and of levetiracetam / placebo, these assessments may be completed within 7 days of the baseline visit.

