This material is the property of the NYU School of Medicine and Langone Medical Center. Do not disclose or use except as authorized in writing by the study sponsor

Study Summary

Title	A 12 week randomized, double-blind, placebo-controlled trial investigating the effects of levetiracetam in early psychosis
Protocol Number	S19-01820
Study Duration	
Months 1-6: Complete regulatory requirements for the R33 trial, train staff at both sites, verify inter-rater reliability and calibrate MRI morphometry between sites. Complete initiation visit at Shanghai Mental Health Center (SMHC). Complete data collection and data management systems.
 
Months 6-29: Enroll 3 subjects per month at SMHC and 1.5 subjects per month at NYUMC to complete the enrollment target of 84 participants in month 26 and last participant completed in month 29. Repeat inter-rater reliability testing and training every 6 months and site visits annually.
 
Months 30-36: Data analysis and manuscript preparation.

Study Center(s)	
Multicenter Study:
 
New York University Langone Medical Center /Bellevue Shanghai Mental Health Center (SMHC)

Objectives	The objectives of this study are to evaluate the efficacy of 12 weeks of Levetiracetam (500 mg) twice daily versus placebo on clinical symptoms, hippocampal volume and cognition and tolerability when added to antipsychotic in early psychosis (EP) patients with treatment-resistant symptoms and to assess the association between hippocampal cerebral blood flow (CBF) and markers of oxidative stress and inflammation with outcomes.
Endpoints / Outcome Measures	
84 treatment resistant early psychosis (EP) subjects will be studied in a two-site, 12-week, double-blind, placebo-controlled trial of levetiracetam 500 mg twice daily added to a stable dose of clinician-determined antipsychotic..
 
 - Change in BPRS total score at 12 weeks is the primary outcome; - Hippocampal volume change measured by MRI prior to the first dose and after 12 weeks and hippocampal CBF measured by arterial spin labeling (ASL) are the secondary outcomes. - In addition, we will measure other clinical symptoms and cognition and will analyze levetiracetam blood levels and biomarkers for oxidative stress and glial injury that predicted hippocampal volume loss in our previous study.

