1.2 Investigational Agent

Levetiracetam is an atypical anticonvulsant that is frequently used in children and adults due to its superior tolerability, ease of use and excellent safety profile [28]. It is rapidly absorbed and rapidly crosses the blood-brain barrier. Maximal blood levels, brain concentrations and antiepileptic efficacy occur approximately 1 hour after oral administration in rodents and in humans [29, 30]. Levetiracetam exhibits linear pharmacokinetics, is not plasma bound, has approximately 100% absorption, and is not metabolized in the liver; it has no reported drug-drug interactions [29]. The half-life of levetiracetam is 6-8 hours; clearance may be slowed in individuals with severe renal impairment [29]. The mechanism of action of levetiracetam is unlike any other anticonvulsant; it binds to synaptic vesicle glycoprotein 2A (SVP2A) [31] which modulates release of neurotransmitter vesicles under conditions of sustained high activation [32]. SVP2A has been genetically linked to schizophrenia [33]. In the hippocampus, levetiracetam reduces neuronal glutamate and dopamine release and enhances GABA release from inhibitory interneurons [32, 34]. Levetiracetam normalized hippocampal hyperactivity and improved hippocampus-dependent memory in aged rats at doses of 5 mg/kg and 10 mg/kg given 40 minutes before testing [35]. In patients with mild cognitive impairment (MCI), levetiracetam 62.5 mg bid and 125 mg bid improved performance and normalized hippocampal BOLD hyperactivation during a pattern separation task [16]. At typical anticonvulsant doses, levetiracetam normalized left and right hippocampal activation patterns during verbal and visual memory tasks in patients with temporal lobe epilepsy (TLE) [36].

The most common side effects reported with levetiracetam are drowsiness, weakness, dizziness and infection (pharyngitis). Mood and behavioral problems have also been reported, including aggression, anxiety, anger, depression, apathy and hostility—these responses appear to be most

CONFIDENTIAL

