The selection of a levetiracetam dose of 500 mg is based on the results of our dose finding trial (i17-00266), in which levetiracetam 500 mg significantly reduced hippocampal CBF and was well-tolerated, whereas levetiracetam 185 mg did not significantly reduce hippocampal CBF. The 500 mg levetiracetam dose is a standard starting antiepileptic dose for partial (temporal lobe) epilepsy; administration of levetiracetam twice-daily will produce mean blood levels similar to those produced two hours after a single dose of levetiracetam 500 mg in our pilot study which were well-tolerated and associated with a reduction in hippocampal CBF. Levetiracetam doses up to 3 g/day are routinely administered in individuals with epilepsy.

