6.3 Baseline (Visit 2 – Day 1)

The following procedures will be performed at Baseline:

CONFIDENTIAL

1. A trained research assistant will complete the BPRS, SANS, CDSS, SAFTEE, MATRICS Cognitive Battery and MRI safety questionnaire (for participants completing the elective MRI scans). A study MD or NP will administer the CSSRS. If the participant is unable to complete MATRICS cognitive testing during the baseline assessment, this can be performed during the first week of study participation.
2. When clinically feasible, study participants will have the option to undergo a 15-30-minute MRI scan to measure blood flow in the brain and to assess brain structure (hippocampal volumetric integrity). Occasionally portions of the scan may need to be repeated due to movement. Participants will also have the option to repeat the 15-30-minute MRI scan two hours after the first dose of study drug to assess the effect of levetiracetam or placebo on hippocampal CBF.
3. Study medication will be dispensed by a study MD or NP or by clinical staff.

Participants will be monitored for 3 hours after the administration of the first dose of medication. Outpatients will be monitored by study MD or NP. Inpatients will be monitored by the clinical staff on the unit.

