6.8 Optional MRI Series to Assess Target Engagement

As mentioned above, the MRI imaging (including the ASL measurement of hippocampal CBF) will be completed when clinically feasible. Participants that are eligible and willing to complete the MRI imaging at Baseline will have the additional option to complete a second scan two hours after study drug administration that duplicates the assessment of target engagement conducted in the preliminary (R61) dose-finding study by measuring the effect of study drug on hippocampal CBF (perfusion).

For these participants, the following procedures will be performed:

1. Study medication will be administered by study MD or NP following baseline imaging
2. Two hours after administration of study medication, the following procedures will be performed
 - a. A trained research assistant will complete the BPRS and SAFTEE assessing symptoms over the last two hours since study drug administration.
 - b. Blood will be drawn (1 milliliter, or 0.25 teaspoons) for assay of levetiracetam levels.
3. Participants will complete a second structural and ASL imaging scan which will take up to 30 minutes total
4. Safety evaluation will be completed by study MD or NP three hours after study drug administration.

Participants will be allowed to smoke cigarettes ad lib prior to and after imaging. Occasionally, portions of the scan may need to be repeated due to movement.

Participants will be eligible for this assessment if they meet the inclusion exclusion criteria for the overarching study and have no contraindications for MRI. The first dose of the study medication will be administered between the two MRI scans, and the first dose of their antipsychotic.

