Appendix 1: Schedule of Events EP Participants

	Screening, Visit 1	Baseline	Week 2	Week 3	Week 4	Week 6	Week 8	Week 12	Follow-Up
	Days -28 to 0	Day 1	Day 6-10	Day 13-17	Day 20-24	Day 34-38	Day 48-52	Day 76-80	Day 85-93
Consent	X								
Authorization Form	X								
Inclusion/Exclusion Checklist	X								
Medical History	X								
Physical Exam	X								

CONFIDENTIAL

This material is the property of the NYU School of Medicine and Langone Medical Center. Do not disclose or use except as authorized in writing by the study sponsor

Psychiatric History	X								
Psychotropic Medication History	X								
DCF	X							X	
SOS	X								
Demographics	X								
EHI	X								
Concomitant Medications	X		X			X		X	
Vital signs	X		X			X		X	X
Anthropometrics	X								
Clinical laboratory assessments (Blood)	X							X	
Biomarkers^		X				X		X	
Urine Drug Screen	X								
Pregnancy Test	X					X			
Randomization		X							
Study drug dispensation		X	X	X	X	X	X	X	
SCID	X								
BPRS	X	X	X	X	X	X	X	X	
SANS		X	X	X	X	X	X	X	
CDSS		X				X		X	
C-SSRS	X	X	X	X	X	X	X	X	
CGI		X	X	X	X	X	X	X	X
BPAQ	X								
Cannabis Use Questionnaire	X					X		X	
Pregnancy Questionnaire	X	X	X	X	X	X	X	X	
SAFTEE		X	X	X	X	X	X	X	X
MCCB*		X				X		X	
Medical Monitoring		X							
Brain Imaging*		X						X	
Levetiracetam blood levels		X**				X		X	
Adverse Event Form		X	X	X	X	X	X	X	X
Study Completion Form									X

* These assessments may be completed within 7 days of the baseline visit.

** These assessments are completed only if participant opts into the optional R61 MRI imaging (see section 6.8)

^ Biomarkers should be collected prior to that day's medication dose

CONFIDENTIAL

This material is the property of the NYU School of Medicine and Langone Medical Center. Do not disclose or use except as authorized in writing by the study sponsor

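### Section 6.7 and the Appendix 1 footnote let the baseline MRI/ASL scan be taken up to 7 days after study drug starts, which would bias the change in hippocampal CBF

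*Protocol*

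**What the plan says.** Section 6.3 places the start of study drug at the baseline visit (Day 1): it is dispensed there, and participants are observed for three hours after the first dose. Section 6.7 says staff will "attempt to complete these assessments prior to the start of antipsychotic medication and of levetiracetam / placebo", and then allows that "these assessments may be completed within 7 days of the baseline visit". The Appendix 1 footnote attached to Brain Imaging and MCCB says the same: "These assessments may be completed within 7 days of the baseline visit".

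Three other places put the scan first:
- The Study Summary (Endpoints / Outcome Measures) lists "Hippocampal volume change measured by MRI prior to the first dose and after 12 weeks". This is worded for volume; the same sentence gives no timing for CBF.
- Section 6.3 lists the scan before dispensing and adds that "Participants will also have the option to repeat the 15-30-minute MRI scan two hours after the first dose of study drug". A repeat after the first dose implies a first scan before it. The same section grants a first-week allowance to MATRICS testing but not to MRI.
- Section 6.8, for the optional target-engagement series, says "Study medication will be administered by study MD or NP following baseline imaging".

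Section 3.2 makes change in hippocampal CBF a secondary outcome. Section 7.3 compares the baseline-to-week-12 difference between arms by a two-sample t-test, and also lists CBF among the endpoints analysed with the primary mixed model and AUC.

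**The concern.** Followed as written, section 6.7 lets a scan taken on study drug serve as the CBF baseline. Only the levetiracetam arm would carry a drug effect in such a scan, so randomisation does not balance the error.

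The protocol's own account makes an early effect likely. Its pilot reports lower hippocampal perfusion two hours after one 500 mg dose, and section 1.4 states that "administration of levetiracetam twice-daily will produce mean blood levels similar to those produced two hours after a single dose of levetiracetam 500 mg". A participant scanned a few days into treatment would therefore probably show much of the effect that the change score is meant to capture.

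Baseline CBF and its change also enter tertiary hypotheses 6 and 8 and the planned correlations. A later analysis plan can set aside an on-drug first scan, but it cannot supply a pre-dose scan that was never taken. Scan timing has to be fixed in the protocol.

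**Working it through.** **Does the text permit an on-drug first scan?** The phrase *within 7 days of* could also cover earlier days. But the sentence in 6.7 sets it as a concession against scanning before levetiracetam or placebo, so it allows scans after the start. The same sentence speaks of scanning before antipsychotics start, although inclusion criterion 4 requires at least 8 weeks of prior antipsychotic treatment. That part of it does not fit this population.

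**Does the conflict reach CBF?** Yes. Section 6.3 describes one session that measures both blood flow and structure, so the timing of the volume scan is the timing of the ASL scan.

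**Pilot figure (section 1.3).** Levetiracetam 500 mg −6.8% (SD 2.6), placebo −1.9% (SD 2.4).
- Difference D = 6.8 − 1.9 = 4.9 points.
- Pooled SD = √((2.6² + 2.4²)/2) = 2.50.
- Effect size = 4.9 / 2.50 = 1.96, which agrees with the stated 2.0.

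**Exposure in the window.** Section 1.2 states linear pharmacokinetics and that "The half-life of levetiracetam is 6-8 hours". Approach to steady state is 1 − 2^(−t/half-life):
- at 24 h: 93.8% (6 h half-life) or 87.5% (8 h);
- at 48 h: 99.6% or 98.4%.

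Most of the 7 days is therefore at near-full exposure.

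**Effect on the t-test.** Let D be the true week-12 difference, f the fraction of scanned levetiracetam participants whose first scan is on drug, and ρ the fraction of D already present at that scan. The levetiracetam baseline mean is lowered by f·ρ·D and the placebo mean is unchanged, so

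contrast in change = D − f·ρ·D = D(1 − f·ρ).

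The protocol gives neither f nor ρ. Taking D = 4.9 as an assumption:

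| f | ρ = 1 | ρ = 0.5 |
|---|---|---|
| 0 | 4.90 | 4.90 |
| 10% | 4.41 (−10%) | 4.66 (−5%) |
| 25% | 3.68 (−25%) | 4.29 (−12.5%) |
| 50% | 2.45 (−50%) | 3.68 (−25%) |

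**Effect on the AUC.** With weights w0 and w12 for Weeks 0 and 12, the raw arm contrast is D(w12 + w0·f·ρ), which exceeds D·w12 whenever f·ρ > 0. The protocol states no weights for CBF. If the trapezoidal rule of section 7.2.1 is applied to two time points, each weight is 6/12 and the contrast is (D/2)(1 + f·ρ). The two planned CBF analyses are thus pushed in opposite directions.

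**Effect on volume.** At the stated annual loss of 6.0%, seven days amounts to 6.0% × 7/365 = 0.115%, which is negligible.

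**The case against.** The counter-case has five parts.

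1. *The conflict is thinner than three places suggest.* The Summary's timing is tied to volume, where the harm is nil. Section 6.8 binds only those who opt into the second scan. List order in 6.3 is not strict, since MATRICS is also listed before dispensing yet may be done later. These limits are real. But 6.3 had to give MATRICS an explicit exception and gave MRI none, it calls the post-dose scan a repeat, and volume and CBF share a session.
2. *The bias has no single direction.* Correct: the change contrast shrinks and the AUC contrast grows. That leaves two distorted analyses of one endpoint. With no true drug effect, neither contrast is biased.
3. *Harm to power is not shown.* This stands. If the true effect were as large as the pilot's, t-test power would stay near 99% at f = 50% with 84 scanned and 83% with 42, ignoring the extra variance from mixing on-drug and off-drug baselines. No power loss is claimed here.
4. *Dropping scans also costs precision.* Signal-to-noise scales by about √(1 − f) if on-drug first scans are dropped from both arms, against 1 − f·ρ if kept. At ρ = 0.5 and f = 25% that is 0.866 against 0.875; at f = 50%, 0.707 against 0.750. So at ρ = 0.5 keeping them is slightly more precise. At ρ = 1 and f = 25% it is 0.866 against 0.75 and dropping wins. This is a cost to state, but it does not justify a biased change estimate.
5. *A week-12 arm contrast needs no baseline scan.* True, and the mixed model can provide it. It is not the change or AUC measure that the protocol names.

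**Conclusion.** The point holds. The protocol contradicts itself on whether the first scan must precede study drug, and section 6.7 as written allows an arm-dependent bias in a named secondary outcome. The t-test contrast in CBF change is multiplied by 1 − f·ρ, and the AUC contrast is inflated.

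The size is unknown. The tabulated losses of 5% to 50% rest on assumed f and ρ, and the values in points also assume that the week-12 effect equals the pilot's two-hour effect. That an early on-drug scan would show the effect is itself an inference: the pilot was single-dose, in medication-free patients, with 17 analysed, whereas this trial enrols patients on antipsychotics. Participants in the optional two-scan series are protected by the order in 6.8. The BPRS primary outcome is unaffected and volume is affected negligibly.

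This should be corrected, but it does not threaten the trial's main conclusion.

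**What to change.** - Reconcile section 6.7, the Appendix 1 footnote and section 6.3 with the Study Summary, so that an MRI/ASL scan counts as baseline only if it was obtained before the first dose of study drug.
- Record the scan time relative to the first dose.
- Exclude a post-dose first ASL scan from the baseline in the main CBF analyses, and add a sensitivity analysis that includes it.
- Leave the first-week MATRICS allowance in section 6.3 as it is, and separate it from MRI in section 6.7 and the footnote.

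The cost is protocol wording, one recorded time and one analysis rule. Some participants in an already optional component will lack a usable baseline CBF scan, with the loss of precision described above. The protocol gives no figure for how many.

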6.8 Optional MRI Series to Assess Target Engagement

As mentioned above, the MRI imaging (including the ASL measurement of hippocampal CBF) will be completed when clinically feasible. Participants that are eligible and willing to complete the MRI imaging at Baseline will have the additional option to complete a second scan two hours after study drug administration that duplicates the assessment of target engagement conducted in the preliminary (R61) dose-finding study by measuring the effect of study drug on hippocampal CBF (perfusion).

For these participants, the following procedures will be performed:

1. Study medication will be administered by study MD or NP following baseline imaging
2. Two hours after administration of study medication, the following procedures will be performed
 - a. A trained research assistant will complete the BPRS and SAFTEE assessing symptoms over the last two hours since study drug administration.
 - b. Blood will be drawn (1 milliliter, or 0.25 teaspoons) for assay of levetiracetam levels.
3. Participants will complete a second structural and ASL imaging scan which will take up to 30 minutes total
4. Safety evaluation will be completed by study MD or NP three hours after study drug administration.

Participants will be allowed to smoke cigarettes ad lib prior to and after imaging. Occasionally, portions of the scan may need to be repeated due to movement.

Participants will be eligible for this assessment if they meet the inclusion exclusion criteria for the overarching study and have no contraindications for MRI. The first dose of the study medication will be administered between the two MRI scans, and the first dose of their antipsychotic.

6.9 Drug and Pregnancy Tests

A rapid urine drug screen and (for individuals assigned female at birth or with childbearing potential of childbearing age) a urine pregnancy test will be conducted by the research coordinator / research assistant or by clinical staff during the screening visit. The rapid urine pregnancy test will be repeated at the week 6 study visit. These results will be reviewed at the time of the visit with the study MD or NP. These results will be confirmed by also submitting urine samples to outpatient labs.

At each study visit, a pregnancy prevention questionnaire will be administered. At the screening, week 6 and week 12 visits, a cannabis use questionnaire will be administered to assess cannabis use.

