common in patients with epilepsy and pre-existing mood disorders. Rare cases of suicidality and of serious dermatologic reactions have also been reported. The median levetiracetam dose in registration trials was 3,000 mg/d administered as a split dose (twice daily) for epilepsy; oral loading doses of 3,000 mg are well-tolerated [29]. Treatment guidelines recommend testing for pregnancy and obtaining a serum creatinine level prior to initiating levetiracetam. Monitoring for behavioral effects (aggression, depression and suicidality) is also recommended—no other laboratory or medical monitoring are recommended.

In summary, levetiracetam is a well-tolerated agent that does not affect metabolism of antipsychotic drugs and normalizes hippocampal hyperactivity by decreasing excessive glutamatergic and dopaminergic transmission, thereby making it an ideal agent to enhance treatment of early psychosis and to prevent antipsychotic toxicity.

1.2.1 Innovative approaches for the measurement of brain atrophy, perfusion and temperature:

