4.2 Exclusion Criteria

1. Current substance abuse / dependence for substances other than nicotine and THC, (i.e. alcohol, amphetamines, barbiturates, etc.)
 - a. A positive urine toxic screen (excluding THC, tricyclic antidepressants, or benzodiazepines (if prescribed)).
 - b. Moderate or severe cannabis use disorder.
2. Diagnosis of major mood disorder or other Axis I disorder other than schizophrenia, schizoaffective disorder or schizophreniform disorder.
3. Current or recent suicidal ideation-- suicidal ideation with intent or plan (indicated by affirmative answers to items 4 or 5 of the Suicidal Ideation section of the baseline C-SSRS) in the 6 months prior to screening or subjects who represent a significant risk of suicide in the opinion of the investigator.
4. Pregnant or nursing or positive urine pregnancy test.
5. Significant medical or neurological illness by history or physical exam, including seizure disorder, history of loss of consciousness related to head trauma or developmental disorder including mental retardation.
6. Renal insufficiency (if serum creatinine greater than laboratory limits for normal, estimated creatinine clearance must be greater than 80).
7. Contraindication to MRI: Metal implants, pacemaker, or other metal in the body or claustrophobia. Individuals with tattoos will be excluded from imaging if tattoos cover more than 5% of the body surface, if a tattoo is greater than 20 cm, or if a tattoo is located on the face, neck or genitals. Individuals with a contraindication to MRI may participate in the trial but will be excluded from the elective MRI component.
8. Significant history of serious violence
 - a. For both inpatient and outpatient subjects, a history of serious violence as assessed by the Buss-Perry Aggression Questionnaire
 - b. For outpatient subjects only, a score of 5 (moderately severe) or higher on the BPRS hostility item at screening or baseline

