6.2 Screening (Visit 1 – Days -28 to 0)

Study Participants will complete a Screening Visit within 28 days of Baseline (Visit 2 – Day 1) to assess eligibility for the study. EP participants will be randomized after eligibility is confirmed during Screening.

The following procedures will be performed at Screening:

1. A study MD or NP will provide potential participants with informed consent documents and will explain the rationale for the study, the procedures, risks and alternatives to participation.
2. Participants will be assessed for inclusion and exclusion criteria.
3. Medical history, including patient demographics, and any concomitant medications use (including over-the-counter medications, vitamins, and supplements) will be reviewed and recorded. The participant's medical record will be accessed to confirm and record all concomitant medications.
4. Psychiatric history will be recorded and a SCID will be conducted by a study MD or NP.
5. Physical examination will be completed by a study MD or NP, or the admission physical exam performed by an NP or MD at Bellevue or NYU Langone will be used. For outpatients, a physical exam performed within 6 months may be used only if no new medical conditions with onset since the physical exam are reported. Vital signs will also be completed by a trained study team member or by the clinical team.
6. A urine pregnancy test and questionnaire will be performed on all individuals assigned female at birth of childbearing potential.
7. A urine drug screen test and cannabis use questionnaire will be performed.
8. Routine laboratory, including electrolytes, creatinine, BUN, glucose and CBC with differential.
9. In addition, the following rating scales will be completed:
 - a. Brief Psychiatric Rating Scale (BPRS) – clinical research coordinator / research assistant
 - b. Columbia Suicide Severity Rating Scale (C-SSRS) – study MD or NP
 - c. Edinburgh Handedness Inventory (EHI) - clinical research coordinator / research assistant
 - i. note EHI can be done at any study visit
 - d. Delusion Classification Form – study MD or NP / clinical research coordinator or research assistant
 - e. Symptom Onset Scale for Schizophrenia – study MD or NP
 - f. Buss-Perry Aggression Questionnaire (BPAQ) – clinical research coordinator / research assistant

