6.6 Visit Scheduling

Participants may complete the screening and baseline visits on the same day. If the screening and baseline visits are completed within 48 hours, then repeated assessments (BPRS and CSSRS) will not be repeated. For participants completing the baseline and screening visits on the same day, the study staff will hold dispensation of the medication until the laboratory results (drug screen, pregnancy test, clinical labs) have been completed and reviewed by a study MD / NP.

To allow for flexibility in the schedule of assessments for scheduling conflicts, holidays, etc., study visits (Weeks 2-12) can be scheduled either one day prior to the scheduled assessment date or within three days after the scheduled assessment date (-1 to +3 days). For example, if a participant completes their Week 3 visit on a Tuesday, the Week 4 visit could be scheduled Monday to Friday of the following week. Study staff will attempt to schedule the visit as close to the intended day as possible.

CONFIDENTIAL

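### No pregnancy test is required at Baseline, so a participant screened on an earlier day can start study drug on a result up to 28 days old and be dosed for 33 to 37 days before the next test

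*Protocol*

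**What the plan says.** Pregnancy is an exclusion. Protocol section 4.2 lists "Pregnant or nursing or positive urine pregnancy test", and inclusion criterion 5a in section 4.1 asks for a negative urine test but sets no maximum age for it. Section 1.2 notes: "Treatment guidelines recommend testing for pregnancy and obtaining a serum creatinine level prior to initiating levetiracetam".

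On timing, section 6.2 says "Study Participants will complete a Screening Visit within 28 days of Baseline" and "EP participants will be randomized after eligibility is confirmed during Screening". Section 6.9 places the urine pregnancy test at Screening and adds: "The rapid urine pregnancy test will be repeated at the week 6 study visit". The Pregnancy Test row of Appendix 1 is marked at Screening and Week 6 only.

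Section 6.3 lists the Baseline procedures. It contains no pregnancy test and goes on to "Study medication will be dispensed by a study MD or NP or by clinical staff", followed by three hours of observation after the first dose.

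Section 6.6 covers participants who have both visits on one day. For them, staff are to "hold dispensation of the medication until the laboratory results (drug screen, pregnancy test, clinical labs) have been completed" and reviewed. The same section contains a rule for two rating scales: "If the screening and baseline visits are completed within 48 hours, then repeated assessments (BPRS and CSSRS) will not be repeated".

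**The concern.** The protocol treats a reviewed pregnancy result as a condition for dispensing when Screening and Baseline share a day, which is when the result is freshest. When Screening was earlier and the result is older, nothing in 6.3, 6.9 or Appendix 1 asks for a new one.

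A pregnancy that was too early to detect at Screening, or that began between Screening and Day 1, would make the participant ineligible. The next scheduled test that could find it is at Week 6. At stake is avoidable drug exposure in someone the protocol means to exclude. This is a participant-safety point. It has no bearing on sample size, power or the primary analysis.

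**Working it through.** **Inputs**
- Screening window: up to 28 days before Baseline (section 6.2); Day -28 to Day 0 in the visit table (section 3.1, Appendix 1).
- Baseline and first dose: Day 1 (section 6.3, Appendix 1).
- Week 6 visit: Day 34 to 38 (section 3.1, Appendix 1).
- Dosing: twice daily (section 5.2).
- Allocation: 2:1 levetiracetam to placebo (section 5.3).
- Site targets: 56 of 84 participants at Shanghai (Study Summary).

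**Age of the pre-dose result.** By the text, at most 28 days. By day numbers, 1 - (-28) = 29 days, because the table counts a Day 0. I use 28.

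**Dosing before the next scheduled test.** Week 6 day minus Day 1:
- earliest: 34 - 1 = 33 days, or 33 x 2 = 66 doses
- latest: 38 - 1 = 37 days, or 37 x 2 = 74 doses

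Read as a full six weeks, Week 6 would be about 42 days, but the printed visit windows give 33 to 37.

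**Longest interval between the two scheduled tests.** 28 + 33 = 61 days to 28 + 37 = 65 days.

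**What stands between an outdated result and the first dose**

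| Safeguard | Where | What it leaves open |
|---|---|---|
| Drug held until the pregnancy result is reviewed | 6.6 | Applies only when both visits are on the same day |
| Outpatient testing at the in-person visit, before baseline assessments | 4.8.1 | Part of the NYU plan; remote screening is optional |
| Hospital results usable if within 36 hours of the study visit | 4.8.3 | NYU and Bellevue inpatients; the study visit may be Screening, so it does not tie the result to the first dose |
| Repeat of assessments after 48 hours | 4.8.1, 4.8.2 | Covers assessments done virtually, not urine tests |
| Abstinence or contraception from Screening | 4.1 (5c) | Depends on adherence; does not reveal a pregnancy already present |
| Pregnancy questionnaire at each visit | 6.9, Appendix 1 | Self-report, not a test |

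The uncovered route is an in-person Screening on an earlier day. It can occur at either site. Section 4.8.1 says that each site will write its own participant protection plan and prints only the NYU one, so for the 56 of 84 participants planned at Shanghai (two thirds) the NYU text gives no assurance.

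**With a Baseline test.** If a negative result from the previous 48 hours is accepted, the pre-dose result is at most 2 days old instead of 28. The longest interval between tests falls from 61-65 days to 33-37 days with a test on Day 1, or 35-39 days (33 + 2 to 37 + 2) if a 48-hour-old result is carried forward.

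**The case against.** The strongest reply is that the schedule contradicts nothing. Sections 6.2, 6.9 and Appendix 1 agree on when tests are done. The guideline cited in 1.2 asks for a test before initiation without limiting its age, and the protocol does test before initiation. The urine drug screen and clinical laboratory tests are likewise done before dosing only at Screening. Contraception, the Baseline questionnaire and the permitted same-day visits leave a narrow gap. All of this stands. It makes the point a cheap improvement to a consistent schedule, not the correction of an internal error. It does not remove the route described above.

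Some stronger readings are tempting, and the protocol does not support them.

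- *That the protocol breaks its own freshness rules.* The 48-hour rule in 6.6 says when two rating scales need not be done twice, and the 36-hour rule in 4.8.3 says when a chart result may stand in for a study test. Neither sets a maximum age for eligibility results before dosing, so 28 days against 48 or 36 hours is not a breach.
- *That a Baseline test would remove nearly all avoidable exposure.* No figure in the protocol supports this. A conception too recent to detect on Day 1 would still be missed, and conceptions after Day 1 are untouched.
- *That 66 to 74 doses means that many doses of levetiracetam.* With 2:1 allocation, one third of participants are expected to be on placebo.
- *That a further test at Week 12 is also needed.* By then only the 9-day taper remains, so it would prevent little exposure.

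**Conclusion.** The point holds as a low-probability safety gap that is easy to close. After an earlier in-person Screening, the protocol permits a first dose on a pregnancy result up to 28 days old and 33 to 37 days of dosing before the next scheduled test. Following the schedule as written could therefore dose a participant whom section 4.2 excludes.

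These figures are upper limits that assume the full 28-day window and the printed Week 6 window; same-day visits reduce the age of the result to zero. How many participants could be affected cannot be stated, because the protocol gives no expected sex split and does not say how many will be screened on an earlier day. Shanghai practice is unknown because its plan is not printed; it may already include a test near the first dose.

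**What to change.** In sections 6.3 and 6.9, add: for participants assigned female at birth, a rapid urine pregnancy test must be negative at Baseline before the first dose, unless a negative result from the previous 48 hours exists. In Appendix 1, mark Pregnancy Test at Baseline with a footnote carrying that exception. The 48 hours is borrowed from 6.6 for convenience, and participants with same-day visits need nothing extra.

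The cost is one urine strip and a little staff time per participant concerned, plus a short amendment. No visit is added, because Baseline already includes biomarker blood and drug dispensing.
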